3 STUDY ENDPOINTS

3.1 Primary

- 3.1.1 The maximum tolerated dose (MTD) of ruxolitinib for the treatment of CMML. The MTD is defined as the highest dose where less than 33% of subjects experience a drug related predefined dose limited toxicity (DLT).
- 3.1.2 Proportion of subject achieving clinical benefit defined as hematologic improvement, complete remission, partial remission, or stable disease by the IWG 2006 criteria (see appendix B)

- 3.2 Secondary
- **3.2.1** Acute myeloid leukemia (AML) transformation according to WHO criteria.
- **3.2.2** Overall survival (OS).
- **3.2.3** Duration of response.
- 3.2.4 The Myeloproliferative Neoplasms Symptom Assessment Form (MPN-SAF) at baseline and at best response.
- 3.2.5 >50% decrease in splenic length as measured by physical exam if applicable
- **3.2.6** The suppression of pSTAT5 intracellular signaling after ruxolitinib in CMML subjects (pretreatment, at 1-2hr post treatment, cycle 2, cycle 4, and progression.)
- **3.2.7** Determine number of colonies formed in the presence of GM-CSF and/or ruxolitinib (pretreatment and progression) as a future predictor of response.
- 3.2.8 Mutational status in our CMML subjects by sanger sequencing of JAK2, c-CBL, N-RAS, K-RAS,RUNX-1, TET2, SRSF2, EZH2, ASXL1, and DNMT3a (pretreatment and progression).
- 3.2.9 Mutational status of JAK2 tyrosine kinase at time of progression by deep sequencing of JAK2 to include M929I, Y931C, G935R, R938L, I960V, E985K. (pretreatment and at progression)

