4.2 Exclusion Criteria

- 4.2.1 Any of the following lab abnormalities:
- 4.2.1.1 Platelet count of less than 35,000/uL
- 4.2.1.2 Absolute Neutrophil Count (ANC) of less than 250 cells/uL
- 4.2.1.3 Serum Creatinine \geq 2.0
- 4.2.1.4 Serum total bilirubin >1.5 x ULN
- 4.2.2 Use of cytotoxic chemotherapeutic agents, or experimental agents (agents that are not commercially available) for the treatment of CMML within 28 days of the first day of study drug treatment.
- 4.2.3 Any serious medical condition or psychiatric illness that will prevent the subject from signing the informed consent form or will place the subject at unacceptable risk if he/she participates in the study.
- 4.2.4 Concurrent use of GM-CSF. G-CSF could be used for the short-term management of neutropenic infection. Stable doses of erythropoietin stimulating agents that were started >8 weeks from first ruxolitinib dose or corticosteroids that were being administered prior to screening are allowed.
- 4.2.5 Uncontrolled current illness including, but not limited to ongoing or active infection, symptomatic congestive heart failure, unstable angina pectoris, cardiac arrhythmia, or psychiatric illness/social situations that would limit compliance with study requirements.
- 4.2.6 History of metastatic malignancy in the preceding 2 years.
- 4.2.7 Pregnant women are excluded from this study because ruxolitinib has not been studied in pregnant subjects. Because there is an unknown but potential risk for

adverse events in nursing infants secondary to treatment of the mother with ruxolitinib, breastfeeding should be discontinued if the mother is treated with ruxolitinib.

4.2.8 Patients who have participated in other interventional (treatment-related) clinical trials within 30 days of enrollment are excluded.

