Dose-limiting toxicity (DLT) is defined as any grade 4 hematologic toxicity and any grade 3 or greater non-hematologic toxicity except nausea that is controlled by antiemetic therapy based on the NCI Common Terminology Criteria for Adverse Events (CTCAE) version 4.0. Criteria for Grade 3 renal toxicity are consistent with prescribing information with respect to renal impairment and safe use of ruxolitinib. Grade 3 metabolic/electrolyte abnormalities that are not clinically significant, and are adequately controlled within 72 hours are not to be considered a DLT. To discern disease specific versus drug specific myelosuppression, Grade 4 thrombocytopenia will be defined as a decrease of $\geq 50\%$ of baseline and a level of $\leq 25,000/\text{uL}$. Grade 4 neutropenia will be defined as a decrease of $\geq 50\%$ of baseline and a level of < 500/uL. Previous clinical trials testing ruxolitinib reported a hematologic nadir of 8 weeks. As such, DLTs during the first and second cycle of therapy, i.e. 8 weeks, will be used for the purpose of deciding the dose for next cohort (see dose escalation schema) but DLTs will continue to be evaluated and reported through all cycles on study. Management and dose modifications associated with the above adverse events are outlined in Section 11.

6.2.1 Dose escalation will proceed according to the following scheme:

Dose Escalation Schedu	ıle

Dose Level	Dose of Ruxolitinib (per day given in equal BID
	doses)
Level 1	10 mg
Level 2	20 mg
Level 3	30 mg
Level 4	40 mg

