6.5.1.5 Blood Products

The use of blood products to include packed red blood cells (PRBCs) and platelet transfusions are permitted and to be given at the discretion of the

treating physician. Recommended guidelines for transfusion include a platelet threshold of 10,000/L for platelet transfusion and a hemoglobin threshold of 8g/dL for PRBC transfusion.

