14 MEASUREMENT OF EFFECT

Definitions:

Response and progression will be assessed according to modified International Working Group (IWG) 2006 criteria²³(Appendix B). Improvements must last ≥ 8 weeks.

• Erythroid Response for pretreatment hemoglobin < 11 g/dl:

 \geq 1.5 g/dL increase in hemoglobin.

For transfused subjects having pre-transfusion baseline hemoglobin ≤ 9 g/dL, a reduction of 4 or more RBC units in the previous 8 weeks compared with pretreatment.

 \circ Platelet response for subjects with a pre-treatment platelet count $< 50 \times 10^9 / L$:

Major platelet response: An absolute increase of $\geq 30 \times 10^9$ /L. If platelets are $< 20 \times 10^9$ /L at baseline, then a 100% increase will qualify as a major platelet response. If subjects are transfusion dependent at baseline, platelet transfusion independence sustained for 8 consecutive weeks will qualify as a major platelet response.

Complete platelet response: increase of platelet count to $\geq 100 \times 10^9/L$ for 8 consecutive weeks.

• Neutrophil response with pretreatment ANC $< 1 \times 10^9$ /L:

 \geq 100% increase and an absolute increase of \geq 0.5 x 10⁹/L

Progression/relapse following hematological improvement: At least one of the following:

Any newly developed (RBC/platelet) transfusion dependence,

 \geq 50% decrease from maximum response levels in granulocytes or platelets, or

Reduction of ≥ 1.5 g/dL hemoglobin.

Complete Response (CR)

Bone marrow: \leq 5% myeloblasts with normal maturation of all cell lines Persistent dysplasia will be noted

Peripheral blood:

Hemoglobin $\geq 11 \text{ g/dL}$

Platelets $> 100 \times 10^9 / L$

Neutrophils $\geq 1.0 \times 10^9/L$

BLASTS < 0%

o Partial Response (PR)

All CR criteria if abnormal before treatment, except:

Bone marrow blasts decreased by $\geq 50\%$ over pretreatment but still $\geq 5\%$

Cellularity and morphology not relevant

Marrow Complete Response (mCR)

Bone marrow: $\leq 5\%$ myeloblasts and decrease by $\geq 50\%$ over pretreatment **Peripheral blood: if HI responses, they will be noted in addition to marrow CR**

Stable Disease (SD)
 Failure to achieve at least PR, but no evidence of progression for > 8 weeks
 Duration of Response:

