District magnency (III D)	9.0 g/dL pretreatment will count in the RBC transfusion evaluation Platelet response (HI-P) Absolute increase of $\geq 30 \times 10^9$ /L for subjects starting with $\geq 20 \times 10^9$ /L						
Platelet response (HI-P) (Pretreatment < 100 x 10 ⁹ /L)	Absolute increase of $\ge 30 \times 10^{7}$ L for subjects starting with $\ge 20 \times 10^{7}$ L Increase from $< 20 \times 10^{9}$ /L to $\ge 20 \times 10^{9}$ /L and by at least 100%						
	At least 100% increase and an absolute increase of > 0.5 x 10 ⁹ /L						
Neutrophil response (HI-N)	At least 100% increase and an absolute increase of > 0.5 x 10 /L						
(Pretreatment $< 1.0 \times 10^9/L$)							

PROGRESSION/RELAPSE CRITERIA FOR SUBJECTS WITH CMML

ALTERING DISEASE NAT	URAL HISTORY					
Disease Progression (PD)	For subjects with:					
	Less than 5% blasts: \geq 50% increase in blasts to $>$					
	5% blasts					
	5%-10% blasts: \geq 50% increase in blasts to \geq 10%					
	blasts					
	10%-20% blasts: \geq 50% increase in blasts to \geq 20%					
	blasts					
	20%-30% blasts: \geq 50% increase in blasts to \geq 30%					
	blasts					
	Any of the following:					
	At least 50% decrement from maximum					
	remission/response levels in granulocytes or					
	platelets					
	Reduction in hemoglobin (Hgb) concentration by ≥					
	2 g/dL					
Disease transformation	Transfusion dependence					
	Transformation to AML (30% or more blasts)					
Relapse after CR or PR	At least one of the following:					
	Return to pretreatment bone marrow blast % Decrement of ≥ 50% from maximum					
	remission/response levels in granulocytes or					
	platelets					
	- Reduction in Hgb concentration by ≥ 1.5 g/dL or transfusion					
	dependence					
HEMATOLOGICAL IMPR						
Progression/relapse after HI	At least one of the following:					
	At least 50% decrement from maximum response					
	levels in granulocytes or platelets					
	Reduction in Hgb by $\geq 1.5 \text{ g/dL}$					
	- Transfusion dependence					

21 APPENDIX C: CYP3A4 Strong Inhibitors

HIV Antivirals:

- -indinavir
- -boceprevir
- -lopinavir/ritonavir
- -ritonavir
- -telaprevir
- -nelfinavir
- -saquinavir

Others:

- -clarithromycin
- -conivaptan
- -grapefruit juice
- -mibefradil
- -posaconazole
- -voriconazole
- -itraconazole
- -ketoconazole
- -nefazodone
- -telithromycin

^{*} Dose reductions as in section 7 are required for strong inhibitors of the CYP3A4.

22 APPENDIX D: Myeloproliferative Neoplasms-Symptom Assesment Form (MPN-SAF)

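### Section 14 and Appendix B define platelet response differently, and only Section 14 credits 8 weeks without platelet transfusion whatever the count

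*Combined protocol and SAP*

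**What the plan says.** Section 3.1.2 defines the primary efficacy endpoint as the proportion of subjects with "hematologic improvement, complete remission, partial remission, or stable disease by the IWG 2006 criteria (see appendix B"). Section 14 says that response follows modified IWG 2006 criteria and also cites Appendix B.

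Section 14 then gives its own platelet rules. They open with "Platelet response for subjects with a pre-treatment platelet count" below 50 × 10⁹/L. A major response is an absolute rise of at least 30 × 10⁹/L, or a 100% rise if the baseline is below 20 × 10⁹/L. A third route follows: "If subjects are transfusion dependent at baseline, platelet transfusion independence sustained for 8 consecutive weeks will qualify as a major platelet response". A complete platelet response needs a count of at least 100 × 10⁹/L for 8 weeks. Duration of response runs from the first major or complete platelet response.

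Appendix B limits HI-P to pretreatment counts below 100 × 10⁹/L. Its entry begins "Platelet response (HI-P) Absolute increase of" 30 × 10⁹/L, for subjects starting at 20 or more. For those starting below 20, the count must cross 20 and rise by at least 100%. Transfusion independence is not mentioned.

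Three other provisions bear on the point:

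- **Entry.** Section 4.2.1.1 excludes a "Platelet count of less than 35,000/uL".
- **Transfusion.** Section 6.5.1.5 leaves transfusion to the treating physician: "Recommended guidelines for transfusion include a platelet threshold of 10,000/L for platelet transfusion". The unit is printed per litre; I read it as per µL.
- **DLT.** Section 6.2 says "Grade 4 thrombocytopenia will be defined as a decrease of" at least 50% from baseline, to 25,000/µL or less. The synopsis prints the same limits as strict inequalities.

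**The concern.** Two passages that claim the same source can give opposite answers for the same subject. The Section 14 route depends on transfusions not being given, and that depends on local practice as well as on platelets. The protocol fixes no pre-study transfusion threshold, so a subject transfused before entry under a more liberal policy could become transfusion-free on study with a lower count than at entry.

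The parallel erythroid rule has two safeguards: a pretreatment hemoglobin condition and a minimum reduction of 4 units. The platelet rule has neither.

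At stake is whether a fall in platelets, possibly drug toxicity, can be recorded as hematologic improvement, enter the phase 2 response count and begin a duration of response. The phase 2 decisions turn on one subject: 1 against 2 responders of 10, and 5 against 6 of 29.

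**Working it through.** **1. The plan's own design figures (Section 15.2).** Inputs: null rate 0.10, alternative 0.30, stop at 1 or fewer of 10, reject the drug at 5 or fewer of 29. Write b(x; n, p) for the binomial probability.

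- Early termination = b(0; 10, p) + b(1; 10, p). At p = 0.10 this is 0.9¹⁰ + 10 × 0.1 × 0.9⁹ = 0.3487 + 0.3874 = 0.736 (stated 0.74).
- Probability of passing = Σ over x = 2 to 10 of b(x; 10, p) × P(Bin(19, p) ≥ 6 − x). At p = 0.10 this is 0.047 (stated 0.05). At p = 0.30 it is 0.805, so the type II error is 0.195 (stated 0.19).

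The design is reproduced.

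**2. The two definitions side by side.**

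| Item | Section 14, major platelet response | Appendix B, HI-P |
|---|---|---|
| Baseline limit | < 50 × 10⁹/L | < 100 × 10⁹/L |
| Rise of at least 30 × 10⁹/L | yes | yes, if starting at 20 or more |
| Starting below 20 × 10⁹/L | 100% rise | 100% rise and crossing 20 |
| Transfusion-independence route | yes, no count condition | none |

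The third row has little practical weight, because entry requires at least 35,000/µL. The first and last rows can change a classification.

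**3. Can a DLT-level count score as a response?** The entry floor and the Section 14 limit leave baselines of 35,000 to below 50,000/µL. Half of that range is 17,500 to below 25,000/µL. Every halving therefore reaches the DLT level while staying above the 10,000 transfusion guideline.

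| Baseline (× 10⁹/L) | Half of baseline | Appendix B needs (baseline + 30) |
|---|---|---|
| 35 | 17.5 | 65 |
| 40 | 20 | 70 |
| 45 | 22.5 | 75 |
| 49.9 | 24.95 | 79.9 |

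Take a transfusion-dependent subject entering at 40,000/µL who stays just under 20,000/µL, untransfused, for 8 weeks. Section 14 scores a major platelet response. Section 6.2 scores grade 4 thrombocytopenia. Appendix B gives no HI-P.

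**4. Does another rule settle it?** Appendix B lists worsening of cytopenias under Failure but does not say that Failure overrides HI. Its 50% decrement rule is measured from the maximum remission or response level, not from baseline. Neither rule is ranked against Section 14.

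**5. Illustrative size.** Assume that a share q of subjects who would otherwise be non-responders qualifies only by this route, and that stable disease is not a response in the Simon test. The null response probability becomes 0.10 + 0.90q.

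| q | Response probability | Type I error | Early termination |
|---|---|---|---|
| 0 | 0.100 | 0.047 | 0.736 |
| 1% | 0.109 | 0.066 | 0.701 |
| 2% | 0.118 | 0.089 | 0.666 |
| 5% | 0.145 | 0.181 | 0.563 |

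The documents supply no value of q.

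**The case against.** The strongest reply is that 3.1.2 already counts stable disease. A subject without progression for more than 8 weeks would be a success with or without the transfusion route. This stands in large part. Under 3.1.2 as written, the route changes the count only for a subject whom Appendix B would otherwise class as Failure or progression. A reader might infer from the table in step 5 that the trial's type I error is in fact 0.09 or 0.18. The documents do not support that: q is assumed, and the calculation excludes stable disease from the tested response.

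A reader might also infer that such subjects would enter the platelet analysis named in Section 15.5. They would not. That analysis concerns complete platelet response, which needs at least 100 × 10⁹/L.

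Other points have partial force:

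- **Rarity.** The case needs platelet-transfusion dependence, an entry count in a narrow band, a halving, and 8 weeks without transfusion. That is probably uncommon.
- **Discontinuation.** Section 9.3 requires study drug to stop after a DLT, so the subject might not spend the 8 weeks on drug. Section 10.2, however, provides for a reduced dose in phase 2 after the same platelet fall. The passages conflict, and neither bars the scoring.
- **Modified criteria.** Section 14 calls its criteria modified, and crediting reduced transfusion need is not odd in itself, since both passages do so for red cells. But Section 14 and 3.1.2 both point to an Appendix B that lacks the modification.
- **Data.** Section 13 requires pre-transfusion counts for the 8 weeks before treatment, so a transfusion-supported baseline can be seen. The scoring rule does not use those counts.

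**Conclusion.** The inconsistency is real and sits in the definition of the primary efficacy endpoint. The transfusion route has no count condition and can only add responders. It permits a DLT-level platelet fall to be scored as a major platelet response that Appendix B would not recognise and might call Failure. It can also start the duration-of-response clock, and that consequence does not depend on how stable disease is handled.

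The effect on the phase 2 decision cannot be fixed from the documents. It is small or nil if stable disease counts as a response and the subject is not classed as Failure or progression. If stable disease does not count, it could be material at low frequencies, because one subject can decide each stage. The documents do not show that error rates are inflated by any stated amount, or that such subjects are expected. The point warrants correction on grounds of consistency and low cost, not because a particular bias has been demonstrated.

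**What to change.** 1. Replace the Section 14 major platelet response rules with the Appendix B HI-P rules, so that the phase 2 response count and duration of response use one count-based definition. Deleting only the transfusion sentence would leave the baseline limit (50 against 100) and the crossing-20 condition unmatched.
2. State that a subject who meets Appendix B Failure or progression is not counted as HI on the basis of transfusion independence.
3. Define platelet transfusion dependence, and report transfusion independence descriptively beside the pre-transfusion and on-study counts. A simple comparison with the pretreatment count is not enough, because that count may be transfusion-supported.
4. Reconcile Sections 9.3 and 10.2 on the handling of a DLT-level platelet fall.

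The cost is wording. Blood counts, the transfusion log and the prior 8 weeks of transfusions are already collected, and the sample size does not change. There are two consequences to accept. A genuine gain in platelet transfusion independence without a count rise would be reported outside the response count. Subjects starting at 50 to below 100 × 10⁹/L, whom Section 14 leaves out, would become assessable for HI-P by a count rise.

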15 STATISTICAL CONSIDERATIONS

15.1 Study Design

This is a phase 1/2, two-stage, sequential cohort dose escalation study. In phase 1, subjects will be allocated to dose levels starting at 10 mg/d (BID dosing) according to the "rolling six" phase I design (see Section 6.2 for the definition of DLT and the dose levels employed and Section 6.4 for the dose escalation

schema). Enrollment to the next dose level will be as per the dose escalation rules table (6.4.1). Subjects who do not complete the first cycles of protocol treatment and drop out of the trial due to any reason other than experiencing a DLT will have to be replaced in order to determine a proper MTD. Phase 1 will continue until MTD is reached. The Phase 2, two-stage, study will enroll a total of 29 patients to determine overall best response at the MTD.

15.2 Sample Size/Accrual Rate

If dose escalation is completed as planned, no more than 53 subjects are expected to enroll onto this study at a rate of approximately 3 subjects every month. For the Phase 2 study the Simon's optimal two-stage design will be employed to test the null hypothesis that response rate (RR) equals to 10% versus the alternative that RR equals to 30%. If the treatment is actually not effective, there is a 0.05 probability of concluding that it is. If the drug is actually effective, there is a 0.19 probability of concluding that it is not. The probability of early terminating the trial at the end of first stage under the null is 0.74. After testing the treatment dose on 10 patients in the first stage, the trial will be terminated if 1 or fewer desired respond. If the trial goes on to the second stage, a total of 29 patients will be studied. If the total number responding is less than or equal to 5, the drug is rejected. A sample size of 29 from Phase 2 produces a two-sided 95% CI with a width equal to 0.38 (±19) when the sample proportion is 0.50 that is the maximum width for a CI with an given sample sizes.

15.3 Statistical Analysis Methods

Demographic and clinical variables for the study patients will be summarized using descriptive statistics (mean, standard deviation, median, inter-quartile range, range, and frequency counts and percentages). Safety and efficacy data will be analyzed overall as well as separately for each dose cohort when appropriate.

15.4 Safety Analysis

This analysis will include all subjects who have received any protocol treatment, regardless of patient eligibility. The number (%) of subjects with adverse events, serious adverse events, and adverse events leading to treatment discontinuation will be reported. Adverse events summary will be reported by type and severity.

Laboratory parameters will also be summarized using descriptive statistics. The number and proportion of subjects with DLTs will be summarized.

15.5 Efficacy Analysis: ITT

This analysis will include all subjects who have received any protocol treatment, regardless of patient eligibility or duration of treatment. Those who have no response assessment data due to reasons such as drop out of the study, withdrawal consent, or lost to follow-up will be treated as non-responders for various response evaluations. The proportion of subjects achieving a complete platelet response will be summarized. A 95% exact binomial confidence interval of the proportion will also be provided for all participants treated at the MTD. In addition, a second analysis of evaluable subjects will be performed. Evaluable subjects are defined as those who complete at least 8 weeks of therapy an complete there first treatment bone marrow biopsy and aspirate to evaluate study drug response.

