15.6 Analyses of Secondary Endpoints

Analyses of the following secondary endpoints will be performed as well:

- 15.6.1 Acute myeloid leukemia (AML) transformation according to WHO criteria.
- **15.6.2** Overall survival (OS).
- **15.6.3** Duration of response.
- 15.6.4 The Myeloproliferative Neoplasms Symptom Assessment Form (MPN-SAF) at baseline and at best response.
- 15.6.5 >50% decrease in splenic length as measured by physical exam if applicable
- **15.6.6** The suppression of pSTAT5 intracellular signaling after ruxolitinib in CMML subjects (pretreatment, at 1-2hr post treatment, cycle 2, cycle 4, and progression.)
- **15.6.7** Determine number of colonies formed in the presence of GM-CSF and/or ruxolitinib (pretreatment and progression) as a future predictor of response.
- **15.6.8** Mutational status in our CMML subjects by sanger sequencing of JAK2, c-CBL, N-RAS, K-RAS,RUNX-1, TET2, SRSF2, EZH2, ASXL1, and DNMT3a (pretreatment and progression).
- **15.6.9** Mutational status of JAK2 tyrosine kinase at time of progression by deep sequencing of JAK2 to include M929I, Y931C, G935R, R938L, I960V, E985K.

(pretreatment and at progression)

We recognize that this is mainly a phase I study with an extension phase at the MTD. However, preliminary data on the above endpoints will prove to be very useful for further investigation of this protocol's treatment. Such data will be summarized appropriately focusing mostly on the subjects treated at the MTD dose in an exploratory fashion. Both point estimates and 95% confidence intervals will be reported, if feasible. Time-to-event endpoints such as OS will be summarized using the Kaplan-Meier product-limit method.

16 Laboratory Correlates

Unless otherwise specified, all laboratory correlates will be performed in the laboratory of [name] under the direction of Drs [name] and [name].

H.LEE MOFFITT CANCER CENTER

CC: [name]

STABILE RESEARCH BUILDING

SRB-2

[name]

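### Section 15.5 ties the reported efficacy proportion and its exact 95% CI to complete platelet response instead of the phase 2 primary endpoint, and Section 14 starts duration of response only at a platelet response.

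*Combined protocol and SAP*

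**What the plan says.** **Efficacy analysis.** Section 15.5 counts all treated patients and treats those without response data as non-responders. It then names one proportion: "The proportion of subjects achieving a complete platelet response will be summarized". The interval follows at once: "A 95% exact binomial confidence interval of the proportion will also be provided for all participants treated at the MTD". The section adds a second analysis in evaluable patients but names no other outcome.

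**Primary endpoint.** Section 3.1.2 gives "Proportion of subject achieving clinical benefit defined as hematologic improvement, complete remission, partial remission, or stable disease" by IWG 2006, with Appendix B holding the criteria. The synopsis lists the same four categories in slightly different words.

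**Design.** Section 15.1 says "The Phase 2, two-stage, study will enroll a total of 29 patients to determine overall best response at the MTD". Section 15.2 sets a Simon two-stage design to "test the null hypothesis that response rate (RR) equals to 10% versus the alternative that RR equals to 30" per cent. It stops with 1 or fewer responders in 10 and rejects the drug with 5 or fewer in 29. It adds: "A sample size of 29 from Phase 2 produces a two-sided 95% CI with a width equal to 0.38", taken at an observed proportion of 0.50.

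**Secondary endpoints.** Sections 3.2 and 15.6 list nine. Duration of response is one of them; complete platelet response is not. For this list Section 15.6 says: "Both point estimates and 95% confidence intervals will be reported, if feasible".

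**Platelet response and duration.** Section 14 places complete platelet response (a rise to at least 100 x10^9/L for 8 consecutive weeks) under a heading for pre-treatment counts below 50 x10^9/L. It starts duration of response when the criteria for a major or complete platelet response are met, whichever is recorded first. It ends duration at marrow progression, or at relapse after CR, marrow CR, PR or HI.

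**The concern.** Followed literally, Section 15.5 produces an estimate and exact CI for an outcome that the trial does not list as an endpoint. The phase 2 primary proportion gets a go/no-go rule but no specified estimate or interval. A statistician would probably report the primary proportion anyway, but that would depart from the written plan.

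Duration of response has a related fault. Its end events cover every type of response, and its start covers one. A patient who responds without a platelet response as Section 14 defines it, for example by erythroid or neutrophil improvement, has an end date but no start date.

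**Working it through.** **1. The plan's own figures.** Inputs from Section 15.2: null 0.10, alternative 0.30, boundaries 1/10 and 5/29.
- Early stopping under the null: P(X ≤ 1 | n = 10, p = 0.10) = 0.9^10 + 10 × 0.1 × 0.9^9 = 0.349 + 0.387 = 0.736 (stated 0.74).
- P(pass | p) = sum over x = 2 to 10 of P(X1 = x) × P(X2 ≥ 6 − x), with X1 ~ Bin(10, p) and X2 ~ Bin(19, p). This gives 0.047 at p = 0.10 (stated 0.05) and 0.805 at p = 0.30, so the type II error is 0.195 (stated 0.19).
- CI width at n = 29. Clopper-Pearson limits are the 0.025 quantile of Beta(x, n − x + 1) and the 0.975 quantile of Beta(x + 1, n − x). For 14/29 they are 0.294 and 0.675, a width of 0.380. The Wald width is 2 × 1.96 × √(0.25/29) = 0.364. The stated 0.38 matches the exact interval.

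The design figures reproduce. The width in 15.2 is that of an exact interval for the phase 2 proportion, whereas 15.5 attaches its exact interval to complete platelet response.

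**2. Is the primary estimate specified elsewhere?**
- 15.1 states the aim of phase 2 and gives no estimator.
- 15.2 gives a decision rule and a planning width.
- 15.3 lists counts and percentages as summaries for demographic and clinical variables and says efficacy data will be analysed overall and by dose cohort. It names no outcome or interval.
- 15.5 mentions several response evaluations, but only in its missing-data rule.
- The CI sentence in 15.6 belongs to the secondary endpoints.

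The intent to estimate response is visible. The sentence that specifies the estimate is missing.

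**3. How complete platelet response relates to the primary endpoint.**
- If the below-50 heading governs it, any qualifying patient rises by more than 100 − 50 = 50 x10^9/L. That satisfies HI-P in Appendix B (a rise of at least 30 from a start above 20, or at least a doubling from below 20 to above 20). It is then a component of HI. Section 4.2 excludes "Platelet count of less than 35,000/uL", so at screening the group is roughly 35 to below 50 x10^9/L.
- If the heading does not govern it, a rise from 80 to 100 would count. That rise of 20 is not HI-P.

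On neither reading is it the Section 3.1.2 proportion.

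**4. Illustration of size (exact 95% CI).** The smallest passing result is 6/29. The documents do not give the number of complete platelet responders, so the other rows are assumptions.

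| Count | Proportion | Exact 95% CI |
|---|---|---|
| 6/29 (smallest Simon pass) | 20.7% | 8.0–39.7% |
| 0/29 platelet | 0% | 0–11.9% |
| 1/29 platelet | 3.4% | 0.1–17.8% |
| 3/29 platelet | 10.3% | 2.2–27.4% |
| 6/29 platelet | 20.7% | same as the first row |

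**5. Denominator.** Section 15.5 takes everyone treated at the MTD. Section 5 adds the phase 2 patients to a phase 1 cohort of up to 6, so the denominator could reach 29 + 6 = 35. Six responders in 35 is 17.1% (6.6–33.6%).

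**6. Duration of response.**

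| Response | End event in Section 14 | Start date in Section 14 |
|---|---|---|
| CR, marrow CR, PR | yes | only with a platelet response |
| HI, platelet | yes | only if Section 14's definition is met |
| HI, erythroid or neutrophil | yes | only with a platelet response |

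**The case against.** The strongest reply is that the intent is clear. Sections 15.1 to 15.3 all point to a response estimate, and complete platelet response can be a component of the primary composite, so it is not foreign to it. Duration of response is exploratory, and Section 13.5 already collects the dates of first response and of loss of response, so no data would be lost. All of this stands, and it limits the size of the point. It does not remove it, because both sections state a rule, and the rule as stated gives the wrong quantity or none.

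Four stronger readings are tempting, and the documents do not support them.
- A reader might infer that the go/no-go decision or its power is compromised. Section 15.2 applies the Simon rule to a response rate and nowhere to platelet response.
- A reader might infer that the Section 15.5 figure will be far below the response rate. Neither the baseline platelet distribution nor the number of platelet responders is given, and the illustrated range ends at no difference.
- A reader might treat 35 to below 50 x10^9/L as a hard cap out of 29. The exclusion is a screening value taken up to 4 weeks before treatment, the below-50 heading can be read as not governing that line, and the denominator may exceed 29.
- A reader might infer that stable disease or marrow CR must be dropped from the count. Section 3.1.2 lists stable disease, and Section 14 classes marrow CR as a pathologic response. Whether either counts in the Simon rule is a separate decision for the sponsor.

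**Conclusion.** The point holds as a fault of specification that should be fixed. Section 15.5 attaches its only named proportion and its exact CI to an outcome that is at most a component of HI, and no section specifies the estimate and interval for the phase 2 primary proportion. Section 14 leaves responders without a platelet response with no start date for duration of response.

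The Simon boundaries, the 29 patients, the type I error and the power are unaffected. No expected numerical difference is claimed: the illustration assumes 0 to 6 complete platelet responders and a denominator of 29, neither of which Section 15.5 fixes. Confidence in the textual finding is high, because it rests on the wording of Sections 3, 14 and 15 alone.

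**What to change.** 1. **Section 15.5.** Replace complete platelet response with the Section 3.1.2 primary endpoint, assessed by Appendix B, and give its exact 95% CI. Where the responses counted in the Simon 1/10, 5/29 rule differ from that endpoint, report that proportion too, with its own exact 95% CI. State the denominator: the 29 phase 2 patients at full accrual. Report any pooled estimate that includes phase 1 patients treated at the MTD separately and label it as pooled.
2. **Section 14.** Start duration of response on the first date that any response with a listed end event is met: CR, marrow CR, PR or any HI. Use the date of first response already recorded under Section 13.5.

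The cost is two text changes. No new data or visits are needed, and the sample size and boundaries stay as they are.
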